7.2.2. Derived and transformed data

When the units of data from laboratories of different sites are inconsistent, the data will be converted according to international standard units.

For laboratory data, if the same parameter is measured multiple times on the same day, the average value of multiple measurements will be used as the measurement this day for analysis.

Duration of exposure to drug (day) = date of the last dose - date of the first dose + 14.

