9.4. Other Safety Assessments

9.4.1. Safety Laboratory Tests

The hematology stipulated in the protocol will be performed in the central laboratory, and blood biochemistry and urinalysis performed in the local laboratory (if they can not be performed in the local laboratory, the samples will be sent out to the central laboratory for detection). Blood samples will be collected, processed and transported in accordance with the instructions of the central laboratory. If the laboratory results are abnormal or clinical symptoms appear, the investigator can collect additional samples for retesting as appropriate to ensure safety. The required laboratory assessments are listed in the table below.

Table 9.1 Safety Laboratory Tests

Hematology	Blood biochemistry	Urinalysis
White blood cell count	Sodium	Bilirubin
Hemoglobin	Potassium	Red blood cells
Hematocrit	Calcium	White blood cells
Red blood cell count	Chlorine	Glucose
Platelet count	Serum urea/urea nitrogen	Ketone
Neutrophil percentage	Creatinine	Nitrite
Lymphocyte percentage	Glucose	pH
Monocyte percentage	Total protein	Protein
Basophil percentage	Albumin	Urine specific gravity
Eosinophil percentage	Total bilirubin	Urobilinogen
Absolute neutrophil count	Alanine aminotransferase	Microscopic examination (if necessary)
Absolute lymphocyte count	Aspartate aminotransferase	
Absolute monocyte count	γ -glutamyltransferase	
Absolute eosinophil count	Alkaline phosphatase	
Absolute basophil count	Lactate dehydrogenase	
	Creatine phosphokinase	
	Total cholesterol	
	Low-density lipoprotein	
	High-density lipoprotein	

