7.5.3. Laboratory test results

Analysis will be performed based on SS1, SS2 and SS3. Analysis will not be performed using SS3 by visit.

The hematology, blood biochemistry and urinalysis parameters at baseline and each visit and their changes from baseline at each visit will be summarized by descriptive statistics.

The number and percentage of subjects whose hematology, blood biochemistry and urinalysis parameters at baseline and each visit are below, within and above the normal range will be summarized.

Pre-treatment and post-treatment laboratory test results are classified into abnormal with clinical significance, abnormal without clinical significance, normal, and not tested in an order of abnormal with clinical significance > abnormal without clinical significance > normal > not tested. Then shift tables are generated. The shift tables are generated based on CTCAE 5.0.

All laboratory test results and abnormal laboratory test results for hematology, blood biochemistry, urinalysis and urine pregnancy will be tabulated.

Qualitative laboratory test results will be summarized by visit. The number and percentage of subjects for each category will be calculated and tabulated.

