7.2.2. Derived and Transformed Data

When the units of data from laboratories of different sites are inconsistent, the data will be converted according to international standard units.

Apart from the calculation of study endpoints based on the data collected from CRF, other data will not be derived or transformed.

Duration of exposure to drug (day) = date of the last dose - date of the first dose + 14.

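### Averaging same-day repeat laboratory values, with no exception for categorical tables, can move an abnormal result into range in the per-visit counts

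*SAP*

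**What the plan says.** The updated SAP, 7.2.2, gives one rule for laboratory data: "if the same parameter is measured multiple times on the same day, the average value of multiple measurements will be used". The average "will be used as the measurement this day for analysis". No type of output is exempted.

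SAP 7.5.3 then plans three kinds of laboratory summary:

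- descriptive statistics for values and changes by visit;
- numbers of subjects below, within and above the normal range at baseline and each visit;
- shift tables from before to after treatment.

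For the shift tables, results are "classified into abnormal with clinical significance, abnormal without clinical significance, normal, and not tested in an order of abnormal with clinical significance" downwards, that is, worst first. The next sentence adds: "The shift tables are generated based on CTCAE 5.0". The same section tabulates all results and all abnormal results, and summarises qualitative results separately by visit.

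On repeat testing, Protocol 9.4.1 states: "If the laboratory results are abnormal or clinical symptoms appear, the investigator can collect additional samples for retesting as appropriate to ensure safety". It gives no timing. The investigator marks the clinical significance of each abnormal value on each laboratory report.

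SAP V1.0, 7.2.2, had no averaging rule. It said that, apart from study endpoints, "other data will not be derived or transformed".

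**The concern.** On-study repeats are not a random sample of results. The protocol names an abnormal result as one trigger for a retest, so a rule that acts only on days with repeats acts more often on days with an abnormal value. Averaging suits a mean-and-SD table. In a count of subjects outside the normal range it can turn an observed abnormal result into a normal one.

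At stake is whether the range counts, and possibly the shift tables, show every abnormal result seen. If they do not, they may disagree with the listings and adverse event tables drawn from the same data. No efficacy endpoint is affected.

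**Working it through.** The documents attach no figure to this rule, so there is none to reproduce. The check has four steps.

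**1. Direction.** The mean of same-day values is never more extreme than the worst of them. If all values are in range, so is the mean. If one is out of range, the mean may or may not be. Compared with keeping the worst same-day result, averaging can only lose abnormal results from the range counts.

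**2. When a result is lost.** Let f be a first value above cut-off c, and r the same-day retest. The average is at or below c when (f + r)/2 ≤ c, that is, r ≤ 2c − f. With c = 1.0 x ULN:

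- f = 1.1: lost if r ≤ 2.0 − 1.1 = 0.9
- f = 1.2: lost if r ≤ 2.0 − 1.2 = 0.8, since (1.2 + 0.8)/2 = 1.0
- f = 1.5: lost if r ≤ 2.0 − 1.5 = 0.5

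Mildly raised values are the ones at risk.

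**3. How often, given a same-day retest.** The documents give no same-day correlation, so it is assumed to lie between 0.5 and 0.95. Pairs are bivariate normal (for example on the log scale), the upper limit is the 97.5th centile, and 4,000,000 pairs were simulated at each correlation. Among pairs whose first value is high:

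| Assumed correlation | Average falls within range | Retest higher than first value |
|---|---|---|
| 0.5 | 67% | 9% |
| 0.7 | 50% | 17% |
| 0.8 | 39% | 22% |
| 0.9 | 26% | 30% |
| 0.95 | 17% | 36% |

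If each result is classified before any averaging and the worst is kept, the loss is 0%. These shares apply only to high values retested on the same day. They are not shares of all abnormal results.

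**4. Reach of the rule, output by output.**

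- *Range counts:* these need one numeric value per subject and visit. With 7.2.2 as written, that value is the average.
- *Shift tables:* the listed categories rest on the investigator's mark on each single report. An averaged value carries no such mark, and a worst-first order points towards keeping the worst result. The CTCAE sentence points instead to numeric grading, where the average could enter. The SAP does not say which basis applies.
- *Listings:* 7.5.3 tabulates all results, so the individual values should remain visible.
- *AESI:* AST/ALT above 5 x ULN is collected as an adverse event (Protocol 10.4.3; SAP 4.2.2), and 7.2.2 does not touch it.

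**The case against.** The strongest objection is that averaging may be the more accurate choice. Under the model in step 3, the underlying value for the day was truly within range in about 82% to 98% of the first-abnormal results averaged back into range. Averaging then mostly removes false abnormals, while worst-value handling keeps them. The rule is also the same in both arms. This stands as a statement about measurement error under assumed inputs. It does not settle the matter for a safety table, where keeping a false abnormal is usually the more acceptable error.

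A second objection is that same-day retests may be rare. Protocol 9.4.1 gives no timing, and "The hematology stipulated in the protocol will be performed in the central laboratory", so some repeats will fall on a later day and escape the rule. The only retest the protocol does time, the screening retest (7.2, exclusion criterion 2g), must be on another day. This also stands and limits the size. However, the on-study provision carries no such restriction, so same-day retests remain permitted.

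A reader might infer several stronger points that the documents do not support:

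- *That averaging is fixed to come before all classification and so biases the shift tables.* No order is stated, and the shift categories themselves rank worst first.
- *That a liver signal can vanish.* Values of 6.0 and 3.0 x ULN average 4.5 x ULN, which still counts as above range. SAP 7.5.3 plans no laboratory table at 5 x ULN, and the event is captured as an AESI.
- *That every average lies nearer normal than the first value.* It does so on balance, but the retest was higher in 9% to 36% of simulated cases. The certain direction is relative to the worst value.
- *That same-day values will mix two laboratories' ranges.* For biochemistry and urinalysis the central laboratory is a fallback when the local one cannot run the test, not a planned duplicate.
- *That the rule should have been listed in SAP 7.8.* That section records departures from protocol analyses, and the protocol has no same-day rule to depart from.
- *That qualitative results would be averaged.* An average can apply only to numeric results, and 7.5.3 handles qualitative ones separately.

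**Conclusion.** The point holds for the range counts. As written, 7.2.2 can move an abnormal laboratory value into range in the per-visit below/within/above counts, and it can never do the reverse relative to keeping the worst same-day result. For the shift tables the finding is an ambiguity: the order of averaging and classification is not stated, and the clinical-significance and CTCAE bases are not reconciled.

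The overall size cannot be derived from the documents, because the number of same-day repeats is not given; it is probably small. Among high values that are retested on the same day, 17% to 67% would be counted as within range under assumed correlations of 0.95 down to 0.5. The conclusion rests on two readings: that the day's measurement for analysis includes categorical analysis, since no exception is made, and that same-day retests occur, which the protocol permits but does not require. The effect is limited to summary tables. It is worth correcting because the correction is simple and the outputs are safety outputs.

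**What to change.** In SAP 7.2.2, limit same-day averaging to the descriptive summaries of continuous laboratory values. For the range counts and shift tables, classify each result individually against the range of the laboratory that produced it, then take the worst same-day category. State that classification comes before any averaging.

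In 7.5.3, say whether the shift tables use the investigator's clinical-significance categories, CTCAE 5.0 grades, or both in separate tables. Confirm that listings show every same-day value.

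The cost is a few sentences and a small programming change. The downside is that a few more abnormal values, some due to measurement error, may appear in the tables; the full listing lets a reader see the accompanying repeat.

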7.3. Study Subjects

7.3.1. Subject disposition

Screening and randomization of subjects will be summarized based on Screening Set 1. The number and percentage of subjects will be calculated, and the reasons for screening failure will be presented; in addition, study drug discontinuation and study termination in both stages will be summarized based on RS1 and RS2, respectively, and the number and percentage of subjects will be calculated. Subject disposition will be tabulated.

7.3.2. Protocol deviations

All subjects who have protocol deviations in Stage 1 will be summarized based on RS1, the number and percentage of subjects will be calculated and tabulated. In addition, all subjects with protocol deviations that have occurred from Stage 2 to end of study will be summarized based on RS2, the number and percentage of subjects will be calculated and tabulated.

7.3.3. Analysis datasets

The subjects who are included to SS1, FAS1, and PPS1 will be summarized based on RS1, and the number and percentage of subjects will be calculated.

The subjects who are included into SS2, FAS2, and PPS2 will be summarized based on RS2, and the number and percentage of subjects will be calculated.

SS3 will include all subjects who have received at least one dose of the study drug. The total number of subjects included into SS3 as well as the specific number of subjects in each treatment group (See Table 4. Analysis Population, Treatment Group and Analysis Stage) will be listed.

7.3.4. Demographics and baseline characteristics

The primary analysis will be performed based on RS1, and Stage 2 analysis will be performed based on RS2.

Demographics such as age, gender, body height, body weight, and BMI will be summarized by descriptive statistics. The severity (moderate [IGA = 3] and severe [IGA = 4]) of atopic dermatitis (AD) at baseline will be summarized, and the number of percentage of subjects will be calculated. The baseline EASI/PP-NRS/BSA/SCORAD/POEM/DLQI will be summarized by descriptive statistics. Demographics and baseline characteristics will be tabulated.

7.3.5. Medical history of subjects

The primary analysis will be performed based on RS1, and Stage 2 analysis will be performed based on RS2.

Medical history will be coded based on Medical Dictionary for Regulatory Activities (MedDRA), and the number and percentage of subjects will be summarized by System Organ Class (SOC) and Preferred Term (PT). Medical history of allergic diseases and allergy history will be summarized separately, and the number and percentage of subjects will be calculated. Medical history will be ranked in descending order of total number of subjects by SOC and PT. All medical histories will be tabulated, and medical history of allergic diseases and allergy history will be tabulated separately.

7.3.6. Prior medication, concomitant medication, and prior and concomitant non-drug therapies

The primary analysis will be performed based on RS1. Stage 2 analysis will be performed based on RS2 (only concomitant medications and treatments in Stage 2).

Prior and Concomitant Medications

Prior medication refers to a non-study drug that is started and ended before the first dose of study drug. Concomitant medication refers to a drug that is started at the time of or after the first dose of study drug, or a drug that is started before the first dose of the study drug and continued after the first dose of the study drug.

Prior and concomitant medications will be coded based on World Health Organization Drug Dictionary (WHODrug), and summarized based on ATC Level 2, ATC Level 4 (if the code is missing, it will be analyzed with the code of previous level) and PT. The number and percentage of subjects will be calculated. Prior and concomitant medications will be ranked in descending order of total number of subjects by ATC Level 2, ATC Level 4 and PT. In addition, they will be tabulated.

Prior and Concomitant Non-drug Therapies

Prior non-drug therapy refers to a therapy that is started and ended before the first dose of study drug. Concomitant non-drug therapy refers to a therapy that is started at the time of or after the first dose of study drug, or a therapy that is started before the first dose of the study drug and continued after the first dose of the study drug.

Prior and concomitant non-drug therapies will be coded by MedDRA. Concomitant non-drug therapies will be summarized by PT. The number and percentage of subjects will be calculated. Prior and concomitant non-drug therapies will be ranked in descending order of total number of subjects. They will be tabulated.

Rescue Treatment

Rescue treatments during treatment period of Stages 1 and 2 will be summarized based on ATC Level 2, ATC Level 4 (if the code is missing, it will be analyzed with the code of previous level) and PT. The number and percentage of subjects will be calculated. These rescue treatments will be ranked in descending order of total number of subjects by ATC Level 2, ATC Level 4 and PT. They will be tabulated.

7.4. Efficacy Analysis

Efficacy analysis in Stage 1 will be performed based on FAS1 and PPS1, mainly the FAS1.

In order to control the type I error rate for multiplicity, a fixed-sequence method will be used. First of all, the active treatment group and the placebo group will be compared for the primary efficacy endpoint; when the primary efficacy endpoint reaches statistical significance, the active treatment group and the placebo group will be compared for the key secondary efficacy endpoints according to the sequence specified in the protocol.

Efficacy analysis in Stage 2 will be performed based on FAS2.

7.4.1. Visit window of efficacy analysis

For scheduled visits, the visit window for efficacy analysis will be based on the visit where the original data are collected. For unscheduled visits and premature withdrawal visit, the visit window for efficacy analysis will be based on the visit closest to the reference date (the previous visit when the distance is the same).

7.4.2. Intercurrent events and handling strategies

See table below for intercurrent events and handling strategies of the primary analysis:

Label	Intercurrent event	Strategy	Remarks
Intercurrent event 1 (use of prohibited drugs/treatments specified in the protocol for which the study treatment must be early terminated due to poor response)	
• Dupilumab or any anti-IL-4Rα or IL-13 antibodies;• Topical PDE-4 inhibitors or JAK inhibitors;• Systemic treatment with corticosteroids or other immunosuppressive and/or immunomodulatory agents, such as cyclosporine, mycophenolate mofetil, azathioprine, methotrexate, or oral JAK inhibitors;• Cell depletion agents (e.g., rituximab) or other biological agents;• Other investigational drugs (non CBP-201) or treatments. 
Due to the poor response, the above prohibited drugs/treatments have been used before the W16 visit.
	Composite strategy	
This type of intercurrent event occurs because of poor response, should be treated as non-response.
 
If it is a continuous variable, the data after the occurrence of the intercurrent event should be imputed with WOCF.

Intercurrent event 2 (use of other prohibited drugs/treatments specified in the protocol other than those in Intercurrent Event 1, with a	
• Initiation of SIT, or dose up-regulation;• TCS or TCI;• Phototherapy (NBUVB, UVB, UVA1, PUVA), sunbed or any other LED therapies;• Bleaching baths more than 2 times a week;• Any drug for the treatment of AD (except	Treatment policy strategy	
The impact on the assessment of efficacy endpoints can be ignored, and the actual observed value is used. If the actual observed value is missing, it will be processed

Label	Intercurrent event	Strategy	Remarks
negligible impact on the assessment of the primary endpoint)	
mild emollients) that may interfere with the evaluation of efficacy results or affect the evaluation of AD severity.
 
The cumulative duration of use of the above prohibited drugs/treatments before the W16 visit is no more than 7 days, and the end date is at least 4 weeks away from the W16 visit.
		according to the principle for processing missing values.
Intercurrent event 3 (use of other prohibited drugs/treatments specified in the protocol other than those in Intercurrent Event 1 due to poor response, with a major impact on the assessment of the primary endpoint)	
 Initiation of SIT, or dose up-regulation; TCS or TCI; Phototherapy (NBUVB, UVB, UVA1, PUVA), sunbed or any other LED therapies; Bleaching baths more than 2 times a week; Any drug for the treatment of AD (except mild emollients) that may interfere with the evaluation of efficacy results or affect the evaluation of AD severity. 
The cumulative duration of use of the above prohibited drugs/treatments due to poor response before the W16 visit is more than 7 days, or the end date is less than 4 weeks away from the W16 visit.
	Composite strategy	
This type of intercurrent event occurs because of poor response, should be treated as non-response.
 
If it is a continuous variable, the data after the occurrence of the intercurrent event should be imputed with WOCF.

Intercurrent event 4 (premature discontinuation of treatment/EOT due to AEs)	The subject experiences an AE or SAE that is considered by the investigator to be intolerable before the W16 visit, and is unsuitable for continuing the study treatment, resulting in premature discontinuation of treatment/EOT.	Composite strategy	
This type of intercurrent event occurs because of poor safety of treatment, should be treated as non-response.
 
If it is a continuous variable, the data after the occurrence of the intercurrent event should be imputed with WOCF.

Intercurrent event 5 (the subject's administration is missing due to the COVID-19 epidemic)	The administration at two consecutive visits (W12 and W14) immediately before the W16 visit is missing or the administration in the Stage 1 treatment period is missing for ≥ 3 times.	Hypothetical strategy	The observed values are not used, and the J2R (jump to reference) method is used for imputation.
Intercurrent event 6 (use of prohibited	The following prohibited drugs/treatments have been used before the W16 visit not because of the poor response:	Hypothetical strategy	The observed values are not used, and the J2R (jump to

Label	Intercurrent event	Strategy	Remarks
drugs/treatments specified in the protocol not for poor response, with a major impact on the assessment of the primary endpoint)	
• Dupilumab or any anti-IL-4Rα or IL-13 antibodies;• Topical PDE-4 inhibitors or JAK inhibitors;• Systemic treatment with corticosteroids or other immunosuppressive and/or immunomodulatory agents, such as cyclosporine, mycophenolate mofetil, azathioprine, methotrexate, or oral JAK inhibitors;• Cell depletion agents (e.g., rituximab) or other biological agents;• Other investigational drugs (non CBP-201) or treatments. 
Or
 
The cumulative duration of use of the following prohibited drugs/treatments not due to the poor response before the W16 visit is more than 7 days, or the end date is less than 4 weeks away from the W16 visit:
 
• Initiation of SIT, or dose up-regulation;• TCS or TCI (topical drugs can be used for AD lesion areas only);• Phototherapy (NBUVB, UVB, UVA1, PUVA), sunbed or any other LED therapies;• Bleaching baths more than 2 times a week;• Any drug for the treatment of AD (topical drugs can be used for AD lesion areas only) that may interfere with the evaluation of efficacy results or affect the evaluation of AD severity.		reference) method is used for imputation.

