12.3. Basis of Sample Size

The sample size of 255 cases (in a 2:1 ratio, 170 cases in the CBP-201 300 mg Q2W group, and 85 cases in the placebo group. Assuming that the dropout rate in the treatment group is 15%, then about 144 cases in the CBP-201 300 mg Q2W group and 72 cases in the placebo group will be able to complete the study) can provide a power of 90% to detect the therapeutic effect on the primary endpoint in the CBP-201 300 mg Q2W group and the placebo group. This power is calculated based on the following assumption: the proportion of subjects reaching the primary efficacy endpoint is 27% in the CBP-201 300 mg Q2W group and 9% in the placebo group, and the significance level for two-sided tests is 0.05.

Based on the results of another conducted phase II international multicenter clinical study of CBP-201 in patients with moderate-to-severe atopic dermatitis, the proportion of subjects reaching the primary efficacy endpoint was 28.1% in the CBP-201 300mg Q2W group and 10.7% in the placebo group, at a two-sided test significance level of 0.05, and if the results of this trial are similar to that of the WW001 trial, the above sample size would provide a power of more than 85% to detect the therapeutic effect on the primary endpoint between the CBP-201 300 mg Q2W group and the placebo group. Therefore, no adjustment is made to the sample size.

The primary analysis of this study will still be based on the 255 subjects enrolled in accordance with V2.1 and its earlier versions of the protocol. Subjects newly enrolled (approximately 81 cases) based on the protocol after V2.1 will not be included in the primary analysis, and only supplementary analysis will be performed.

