7.4.4. Other efficacy endpoint analysis

The categorical efficacy endpoint analysis in Stage 1 will be performed using the same method as the primary efficacy endpoint analysis.

The continuous efficacy endpoint analysis in Stage 1 will be performed using the same method as the secondary efficacy endpoint analysis.

According to the investigator's judgment, AD aggravation or deterioration of symptoms which requires drugs or treatments originally prohibited by the protocol for rescue therapy will be defined as "AD recurrence" event.

The number of AD recurrence, the number of subjects with AD recurrence, and the number of days of AD recurrence in Stage 1, from baseline to W8, from W9 to W16 will be analyzed. The total number of AD recurrence in each stage will be summarized. AD recurrence will be summarized by the number of recurrences, that is, 0, 1, 2 and ≥ 3 . The number and percentage of subjects will be calculated. Chi-squared test will be adopted to compare whether the differences between the two groups are statistically significant. The total number of subjects with AD recurrence in each stage will be summarized, and the number and percentage of subjects will be calculated. Chi-squared test will be performed to compare whether the differences between the two groups are statistically significant. The number of days of AD recurrence in each stage will be summarized by descriptive statistics.

7.4.5. Efficacy analysis in stage 2

During efficacy analysis in Stage 2, the percentage of subjects achieving efficacy endpoint and its confidence interval will be calculated for categorical efficacy endpoints. For continuous efficacy endpoints, ANCOVA model will be used to calculate the mean, the Least Square Mean, 95% confidence interval and SE of the change from baseline and percentage change from baseline of each efficacy endpoint. The model will include treatment group, severity of baseline disease (IGA 3 or 4), and baseline value of corresponding endpoint. Inferential statistics will not be performed during the Stage 2 analysis. The following two analyses will be performed.

Analysis method 1: Categorical efficacy endpoints after the occurrence of events will be regarded as no response for subjects who have the following conditions; continuous efficacy endpoints after the occurrence of events will be imputed using WOCF in Stage 2; other missing data except for the conditions above will be imputed using multiple imputation (MI).

- Group adjustment

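### In Stage 2, subjects who stop for lack of efficacy without qualifying rescue and have no observed endpoint can be imputed as responders, and no Stage 2 analysis tests this

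*SAP*

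**What the plan says.** The Stage 2 efficacy rules are in SAP 7.4.5, in the later of the two SAP versions supplied; version 1.0 left Stage 2 to an update. Method 1 counts a categorical endpoint as non-response, and applies WOCF to a continuous one, after any of three events:

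- group adjustment, meaning the move to Group E of a Group C or D subject who misses EASI-50 at two consecutive assessments (SAP 3.1);
- early stopping because of an AE;
- rescue with prohibited treatment because of poor response, where the second list of treatments counts only beyond 7 cumulative days.

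For the rest, "other missing data except for the conditions above will be imputed using multiple imputation (MI"). Method 2 uses observed values and fills any gap by MI. SAP 7.4.5 specifies no missing-as-failure, reference-based or tipping-point analysis for Stage 2, and it excludes inferential statistics.

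The Stage 1 rules in SAP 7.4.2 have a similar structure. Intercurrent events 1 and 3 need a prohibited treatment taken because of poor response; event 4 is "premature discontinuation of treatment/EOT due to AEs". The reason given for events 1 and 3 is: "This type of intercurrent event occurs because of poor response, should be treated as non-response".

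**The concern.** By the SAP's own rationale, an event that arises from poor response is a failure. Stopping because the drug does not work fits that rationale at least as well as rescue does, yet no rule names it. If the subject takes no qualifying rescue and has no later assessment, the endpoint is simply missing. MI then gives the subject a positive chance of response, while a subject who stops for an AE is a certain non-responder.

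At stake are the descriptive W52 figures: response by group, and the maintenance endpoints listed in SAP 4.1.3, such as EASI-75 or IGA 0-1 kept from W16 to W52. Readers will take these as the evidence on durability. Both Stage 2 methods fill residual gaps by MI, so comparing one with the other would not reveal the problem.

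**Working it through.** **The plan's own figure.** The only stated figure nearby is the Stage 1 power (protocol 12.3): "in a 2:1 ratio, 170 cases in the CBP-201 300 mg Q2W group, and 85 cases in the placebo group", with 144 and 72 completing; "27% in the CBP-201 300 mg Q2W group and 9% in the placebo group"; "the significance level for two-sided tests is 0.05"; and the sample "can provide a power of 90% to detect the therapeutic effect on the primary endpoint". With pooled variance under the null:

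- pooled rate = (144 × 0.27 + 72 × 0.09) / 216 = 0.21
- null SE = √(0.21 × 0.79 × (1/144 + 1/72)) = 0.0588
- alternative SE = √(0.27 × 0.73/144 + 0.09 × 0.91/72) = 0.0501
- z = (0.18 − 1.96 × 0.0588) / 0.0501 ≈ 1.29, so power = 90.2%

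The stated 90% reproduces, and 216/0.85 = 254.1, rounded up to 255. This point does not challenge those figures.

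**Who falls through in Stage 2.** The subject must have stopped for lack of efficacy and meet all of the following:

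1. *No group adjustment.* This leaves Group E, whose members were already non-responders at W16 and have no such route, and Group C or D subjects who stop before a second failed assessment. Investigator assessments are every 4 weeks (protocol 6.2.3.2), so stopping after one failure is possible.
2. *No AE-driven stop and no qualifying rescue.*
3. *No observed endpoint.* Follow-up runs 8 weeks after the last dose (SAP 3.1), so a last dose before about W44 (52 − 8) ends follow-up before W52. A withdrawal visit is mapped to its closest visit (SAP 7.4.1), which need not be W52.

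**Size in Stage 2.** Let f be the share of subjects meeting all these conditions and r their imputed response rate. Counting them as non-responders removes f × r, so the overstatement is f × r. The documents give neither value; both are assumptions.

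- f = 2%, r = 20%: 0.4 points
- f = 5%, r = 40%: 2.0 points
- f = 8%, r = 60%: 4.8 points

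A wider case assumes 70% response among observed subjects, with MI imputing at that same rate. It gives 0.02 × 0.70 = 1.4 points up to 0.15 × 0.70 = 10.5 points for f of 2% to 15%. If MI imputes at half that rate, the range is 0.7 to 5.25 points.

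**Size in Stage 1, for contrast.** Residual missing values are imputed by MI on placebo and by jump to reference (J2R) on CBP-201, so take an imputed rate of about 9% in both arms. With shares fT (CBP-201) and fC (placebo), the planned difference minus the non-response difference is 0.09 × (fT − fC).

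- Equal shares of 5%: planned 26.1% vs 9.0%; as non-responders 25.65% vs 8.55%. The difference is 17.1 points either way.
- 5% on CBP-201 and 15% on placebo: 17.1 points planned against 25.65 − 7.65 = 18.0 as non-responders. The plan is lower by 0.9 points.

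**The case against.** The strongest reply is that the plan already catches most such subjects.

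- Group adjustment is in effect a lack-of-efficacy rule, and it operates on the Group C and D subjects who feed the maintenance endpoints. Group E is tabulated separately (SAP Table 4).
- Worsening of a pre-existing condition after exposure counts as an AE (protocol 10.1.3 and 10.4.1), so stopping for intolerable worsening of AD can fall under the AE condition.
- The early termination and follow-up visits include efficacy assessments (protocol 6.2.4 and 6.2.5), so some late stoppers will have an observed value.
- The Stage 2 imputation covariates are not stated. If earlier scores enter the model, as specified for Stage 1, poor responders would be imputed well below the average rate.

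All of this stands, and it makes f and r smaller. It does not bring them to zero: Group E and early Group C or D stoppers remain, and no Stage 2 analysis bounds the effect.

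A reader might also infer that the Stage 1 primary result is biased in favour of CBP-201. The documents do not support that. J2R draws missing CBP-201 values from the placebo distribution. SAP 7.4.3 plans a missing-as-failure analysis and, for the primary endpoint, a tipping-point analysis. The difference is unchanged when stopping is equal across arms and slightly reduced when placebo subjects stop more often; that last pattern is plausible but assumed.

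**Conclusion.** The gap is real but narrow. In Stage 2, some subjects who stop for lack of efficacy can be credited with a response, contrary to the SAP's rationale for its non-response rules. The W52 rates are then overstated by f × r: 0.4 to 4.8 points at an assumed 2-8% and 20-60%, and near zero if few subjects meet all the conditions or if MI uses their poor earlier scores. These inputs are illustrations, not estimates from the trial.

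It would be wrong to infer that every stop for lack of efficacy escapes the rules, or that a type I error is at risk. Group adjustment and the AE condition catch many such stops, and Stage 2 carries no inference. In Stage 1 the effect is under 1 point in the cases computed, toward the null where placebo stops are more frequent, and covered by planned sensitivity analyses.

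**What to change.** In SAP 7.4.5, method 1, extend the AE-discontinuation condition to early stopping because of an AE *or lack of efficacy*, with non-response for categorical endpoints and WOCF for continuous ones. Use the recorded withdrawal reason, classified without knowledge of the Group C or D assignment. Add one sensitivity analysis for the Stage 2 categorical endpoints that counts every residual missing value as non-response; this needs no classification of reasons.

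The cost is a phrase, one more set of tables, and some classification work. Protocol 7.3 requires the reason for withdrawal to be recorded, but its open list does not name lack of efficacy, and the CRF is not available here to confirm a usable code. Reported rates will be slightly lower. The SAP describes the October 2023 blinded review as already held; if Stage 2 has since been unblinded, the missing-as-non-response analysis can still be run, labelled as added later.

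Leave intercurrent event 4 in Stage 1 as it is. Changing it would alter the primary estimand after the planned Stage 1 unblinding (protocol 6.3.2), for almost no gain.
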